8.2.5. Adverse Event Summaries for the Japanese Population

A subset of the above-mentioned summary will be generated for the Japanese overall population. The complete list is available in Appendix A.

8.3. Clinical Laboratory Tests

8.3.1. Laboratory Value Definitions

The measurement of all laboratory parameters (except pregnancy testing) as indicated in the Protocol will be performed centrally. Laboratory values and change from baseline values will be summarized descriptively by visit. Baseline will be determined according to Section 4.1.3. If there are multiple values that meet the criteria for baseline, additional rules may be provided after consultation with the medical monitor to delineate which value will be defined as baseline.

Laboratory test values will be assessed for severity based on the numerical component of CTCAE v5.

8.3.2. Laboratory Value Summaries

All test results and associated normal ranges from central laboratories will be reported in or converted to SI units.

When there are multiple nonmissing laboratory values for a participant's particular test within a visit window, the convention described in Table 12 will be used to determine the record used for by-visit tabulations and summaries.

Table 12: Identification of Records for Postbaseline By-Visit Summaries

Priority	Laboratory Visit	Proximity to Visit Window	Tiebreaker
1	Scheduled	In-window	Use smallest laboratory
2	Unscheduled	In-window	sequence number
3	Scheduled	Out-of-window	

Shift tables based on the worst postbaseline value recorded will use all postbaseline values occurring within 90 days of stopping study treatment.

Numeric laboratory values will be summarized descriptively in SI units, and non-numeric test values will be tabulated when necessary. In addition, line graphs will be provided for hemoglobin, platelet counts, and neutrophils.

For test results that will be summarized with available normal ranges, the number and percentage of participants with laboratory values being low (but never high), normal, high (but never low), and both low and high will be calculated for each test. This shift summary will be produced for each test for the safety population. The denominator for the percentage calculation will use the number of participants in the baseline category (ie, low, high, normal, missing) as the denominator for the percentage in each of the categories during the study.

The number of participants who experienced worsening of laboratory abnormalities will be summarized by maximum severity.

In cases where differentials of hematology parameters are obtained without corresponding absolute count data, efforts will be made to investigate if the conversion to an absolute value will lead to additional abnormalities. This will be discussed with the clinical team regarding appropriate documentation and action.

8.3.3. Potential Drug-Induced Liver Injuries

Participants with elevated ALT or AST \geq 3 × ULN range and alkaline phosphatase < 2 × ULN range accompanied by total bilirubin \geq 2 × ULN range within \pm 7 days will be listed by treatment group.

8.4. Vital Signs

Values at each scheduled visit, change, and percentage change from baseline for vital signs, including systolic blood pressure, diastolic blood pressure, pulse, temperature, respiratory rate, and weight will be summarized descriptively.

Normal ranges for vital sign values are defined in Table 13. For participants exhibiting vital sign abnormalities, the abnormal values will be listed along with their assigned treatment group. Alert vital signs are defined as an absolute value outside the defined normal range and percentage change greater than 25%. Note that the definition of alert vital signs does not apply for body temperature or weight. The abnormal values for participants exhibiting alert vital sign abnormalities will be listed.

Table 13: Normal Ranges for Vital Sign Values

Parameter	High Threshold	Low Threshold
Systolic blood pressure	≤ 155 mmHg	≥ 85 mmHg
Diastolic blood pressure	≤ 100 mmHg	≥ 40 mmHg
Pulse	≤ 100 bpm	≥ 45 bpm
Temperature	≤38°C	≥ 35.5°C
Respiratory rate	≤ 24 breaths/min	≥ 8 breaths/min

8.5. Electrocardiograms

The INV will evaluate the clinical significance of each ECG value outside the reference ranges (including QTc assessment), according to the nature and degree of the observed abnormality. Any new abnormal values or those deteriorating from baseline considered to be clinically significant should be reported as AEs. The INV-evaluated ECG abnormalities are captured on the "12-Lead ECG" eCRF form. Incidences of such abnormalities and a description of the clinically significant abnormality will be listed with study visit and assigned treatment group.

A 2D-ECHO or cardiac MUGA scan will be obtained at screening to evaluate cardiac function, including assessment of LVEF. This information will be listed.

9. INTERIM ANALYSES

9.1. Overview of Progression-Free Survival Interim Analyses

An IDMC will be involved in reviewing the PFS interim analysis results and will provide their recommendation for a potential nonbinding futility stop based on comparative efficacy and safety data. The IDMC will consist of clinicians and an IDMC statistician. The sponsor will remain blinded, and IDMC decisions will be communicated through sponsor management as dictated in the IDMC charter.

9.1.1. Progression-Free Survival Interim Efficacy Analysis

A PFS interim analysis for futility will be performed after 20% (approximately 35) of the required INV-assessed PFS events have been observed in participants with FL in the FAS. This is expected to occur approximately 15 months after the first participant is randomized and approximately 338 (out of 528 total) participants with FL have been randomized in the study.

The PFS HR will be calculated, and the IDMC may recommend to stop the study if the observed HR of tafasitamab plus lenalidomide in addition to rituximab (TGA) over placebo plus lenalidomide in addition to rituximab (TGB) is ≥ 1.05 for participants with FL in the FAS (nonbinding futility boundary; see Table 14). Early stop for efficacy is not planned.

The false negative rate for a futility stop with a futility boundary of HR = 1.05 is approximately 8% if the true HR is 0.65 and approximately 15% if the true HR is 0.74.

The false positive rate for continuation of the study with a futility boundary of HR = 1.05 is approximately 62% if the true HR is 0.95.

Table 14: Guidelines for Decisions - Progression-Free Survival

	Interim Analysis				
Projected timing	15 months	15 months			
Projected randomized participants	338 participants				
Number of PFS events	35 events				
Decision outcome	Futility Boundary	Continue			
Estimated HR	≥ 1.05	< 1.05			

At the PFS interim analysis for futility, the IDMC will review both efficacy and safety data. The IDMC recommendation to stop the study for futility will be based on totality of evidence including evaluation of the primary endpoint, PFS, as well as other efficacy endpoints including ORR, DOR, PET-CR rate, and OS. Additional operational details of the interim analysis, including tables, figures, and listings provided to the IDMC will be provided in the IDMC charter.

9.1.2. Interim Safety Review

After the first 60 randomized participants (approximately 30 in each treatment group) complete at least the first 2 study treatment cycles (8 weeks), the IDMC will review the safety data to monitor and evaluate the safety of the combination treatment and provide recommendation on whether the combination treatments are safe. Thereafter, the IDMC will review the safety data approximately every 6 months.

Additional operational details of the interim analyses, including tables, figures, and listings provided to the IDMC will be provided in the IDMC charter.

Additional safety analyses may be performed at the discretion of the IDMC chair.

9.2. Overview of Overall Survival Interim Analyses

At the time of the PFS primary analysis, an interim futility analysis of OS will be conducted.

9.2.1. Overall Survival Interim Analysis

To estimate the number of deaths at the time of the PFS primary analysis the same hypothesis as specified in the sample size section will be used (see Section 3.3). A median OS of 10 years in the control group, a PFS HR of 0.65, a 21 months accrual rate, a 12 months follow up, and a 15% drop out rate would result in approximately 47 deaths at the time of the PFS primary analysis estimated 33.5 months after the first participant is randomized.

The final analysis for the study will still be expected to occur approximately 96 months after the first participant is randomized.

The OS interim futility analysis will be implemented using an O'Brien and Fleming beta spending function with the characteristics as presented in Table 15.

Table 15: Guideline for Decision - Overall Survival

Assumed true HR	0.65				
Median OS in control arm	120 months				
Alpha level	One-sided 2.5%				
Power	80%				
Futility rule	Stop for Futility if observed HR > 1.24 (non-binding)				
Futility boundary (z-value scale)	-0.744				
Futility Rule Operating Characteristic	True HR	Probability of reaching futility boundary			
	True HR = 0.65	1.40%			
	True HR = 1	22.85%			
	True HR = 1.25 ^a 52.25%				
	True HR = 1.5a	74.98%			

^a Obtained running 10000 simulations using the get simulation survival function from Rpact with a seed = 1234.

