8.9.3. Survival Follow-Up/Completion of Study

All participants will be followed for survival status every 12 weeks (\pm 4 weeks) until death, lost to follow-up, withdrawal of consent for survival follow-up, completion of the 5-year follow-up interval, or the end of the study.

For participants who have entered the survival follow-up period, sites will continue to collect
data regarding initiation of new anticancer treatment
and report OS. For participants who do not intend to return to the
study investigator for their ongoing care, follow-up will be maintained by telephone contact,
patient records, and public records/databases at intervals of no longer than 12 weeks.

Additional survival assessments may be performed outside the 12-week interval if a survival update is required for an interim assessment to meet safety or regulatory needs.

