8.9.4. End of Study

The end of study will occur after the last participant has completed a minimum of 5 years of post-treatment follow-up. This is expected to occur approximately 8 years after the first participant is enrolled.

The sponsor has the right to terminate the study at any time.

9. ADVERSE EVENTS: DEFINITIONS AND PROCEDURES FOR RECORDING, EVALUATING, FOLLOW-UP, AND REPORTING

Study personnel must remain vigilant for the occurrence of AEs, particularly those that may be life-threatening. Personnel who are trained in the acute management of IRRs, CRS, anaphylaxis, and other emergencies, and who have access to appropriate clinical supplies, should be readily available.

All AEs should be treated appropriately. Such treatment may include changes in study treatment including possible interruption or discontinuation, starting or stopping concomitant treatments, changes in the frequency or nature of assessments, hospitalization, or any other medically required intervention. Once an AE is detected, it should be followed up, and an assessment should be made at each visit (or more frequently, if necessary) of any changes in its severity, its suspected relationship to tafasitamab, lenalidomide or rituximab, any of the interventions required to treat it, and its outcome.

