10.4.1.2.3. Overall Survival in the Follicular Lymphoma Population

Overall survival is defined as the time from randomization until death from any cause. Participants who are not reported as a death at the time of the analysis cutoff will be censored at the date of last known alive, regardless if a new antilymphoma therapy was started.

All participants should be followed until death or until the end of study as specified in the Protocol, whichever comes first. The follow-up data should contain the date the participant was last seen alive/last known alive, the date of death, and the reason of death ("disease progression," "adverse event," or "other").

Overall survival will be compared and analyzed in the same manner as described above in Section 10.4.1.1 for the PFS.

Key secondary analysis of OS will be performed for participants with FL in the FAS. The analysis will be performed at the time of final analysis.

Additional sensitivity analyses will be performed as mentioned in Section 10.4.1.6.

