3.3. Sample Size Considerations

The primary objective of the study is to detect a statistically significant difference in PFS (INV) for the tafasitamab-lenalidomide combination in addition to rituximab relative to placebo-lenalidomide in addition to rituximab for participants with FL.

Based on the assumptions in Table 2, a total number of 174 PFS events in the FL population are required to detect an HR of 0.65 with 80% power at the primary analysis, using a 2-sided, log-rank test at an alpha level of 5% and a 1:1 randomization ratio between the 2 treatment groups. Assuming a median PFS of 27.8 months for placebo-lenalidomide in addition to rituximab (TGB), 21 months of enrollment, 12 months of follow-up for PFS, and 15% of dropouts, 528 evaluable FL participants need to be randomized.

Table 2: Sample Size Assumptions

Primary Endpoint	PFS (INV-assessed) for the FL population
Median PFS in TGA	42.8 months
Median PFS in TGB	27.8 months
Randomization Ratio	1:1
Assumed HR	0.65
Alpha (2-Sided)	5%
Power	80%
Enrollment Duration	21 months
Follow-Up for PFS (Starting From Last Participant Randomized)	12 months
Accrual Rate	0.1 participant/site/month
PFS Events Required at Primary Analysis	174
Total Participants (Without Dropout)	448
Assumed Dropout Rate	15%
Total Randomized Participants	528

A minimum of 60 and up to 90 additional participants with MZL will be randomized at a 1:1 ratio to 1 of the 2 treatment groups. The number of participants with MZL is based on the expected enrollment proportion of participants with FL and MZL.

A 2-stage design with 1 interim analysis for a potential futility stop will be applied (see Section 9.1.1).

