7.3.2.3. Overall Survival in the Follicular Lymphoma Population

Overall survival is defined as the time from randomization until death from any cause. All participants should be followed until death or until the end of study, whichever comes first, as specified in the Protocol.

The cause of death ("disease progression," "adverse event," or "other") will be summarized.

Participants who are not reported as a death at the time of the analysis cutoff will be censored at the earlier of the analysis cutoff and date of last known alive. The last known alive date is defined as the later of the last study visit and the date the participant was last known alive from the "Survival Follow-Up," "End of Treatment," and "End of Study" eCRFs. Partial death dates will be handled using the rules described in Section 4.1.4.

Overall survival will be compared and analyzed using stratified tests as described in Section 7.3 for PFS with FL in the FAS at the time of interim, primary, and final analysis. Participants will be censored at the last date they were known to be alive, regardless if a new antilymphoma therapy was started.

Post-treatment systemic antilymphoma therapies will be summarized and listed.

[figure not shown]

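### SAP Table 15 claims 80% power for OS, but the plan's own inputs give about 149 deaths (75% power) at month 96, or about 129 (69%) if survival follow-up stops near 6 years

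*SAP*

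**What the plan says.** SAP Section 9.2.1 reuses the sample-size assumptions of Section 3.3: 21 months of accrual, 12 months of follow-up and 15% dropout. With a control median OS of 10 years and HR 0.65, the SAP says this "would result in approximately 47 deaths at the time of the PFS primary analysis", at an estimated 33.5 months. It then says: "The final analysis for the study will still be expected to occur approximately 96 months after the first participant is randomized". The OS futility look uses an O'Brien and Fleming "beta spending function with the characteristics as presented in Table 15". Table 15 lists true HR 0.65, control median 120 months, one-sided alpha 2.5%, power 80%, a stop if the observed HR exceeds 1.24 (z = -0.744), and a 1.40% chance of stopping when the true HR is 0.65. Neither document gives a death count for the final OS analysis.

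On dropout, Table 2 of SAP Section 3.3 lists 448 participants without dropout, and the text says that with "15% of dropouts, 528 evaluable FL participants need to be randomized".

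On survival follow-up the documents point two ways:
- **To death or end of study.** Protocol Section 10.4.1.2.3: "All participants should be followed until death or until the end of study as specified in the Protocol, whichever comes first". SAP Section 7.3.2.3 says participants are "followed until death or until the end of study, whichever comes first, as specified in the Protocol". Protocol Section 8.9.4 makes 5 years a minimum tied to the last participant: "The end of study will occur after the last participant has completed a minimum of 5 years of post-treatment follow-up".
- **Limited per participant.** Protocol Section 8.9.3 ends survival follow-up at the earliest of several events, among them "completion of the 5-year follow-up interval, or the end of the study". Protocol Section 4.2 and SAP Section 4.1.5 put a participant's total time on study at about 6 years.

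**The concern.** The interim count of 47 deaths, the 15% dropout, the month-96 final analysis and the 80% power sit together in one section, so they should follow from one set of assumptions. They do not appear to. The interim count looks net of dropout, while 80% power needs about as many final deaths as all 528 participants would supply with no dropout.

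OS is the last endpoint in the alpha-controlled hierarchy, and Table 15 holds the only OS power figure in either document. A non-significant final OS result would be read against that 80%. The same final count also sets the information fraction from which the futility boundary is said to be derived.

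**Working it through.** **Inputs.** From SAP 9.2.1 and Table 15: control median OS 120 months, HR 0.65, one-sided alpha 2.5%, 21-month accrual, interim at month 33.5, final at month 96. From SAP 3.3: 1:1 allocation, 448 participants net of dropout, 528 randomized. Assumed here: exponential survival and uniform accrual.

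**1. What the 15% means.** 448/0.85 = 527.06, in line with the 528 stated. Section 3.3 therefore treats 15% as a one-off proportion.

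**2. Deaths needed for 80% power.** 4 × (1.96 + 0.8416)² / (ln 0.65)² = 169.2, so 170 (Schoenfeld); Freedman's formula gives 175. Table 15 points to the same target: setting its 1.40% equal to the spending function 2 × [1 − Φ(z₀.₉/√t)] gives t = 0.272, and 47/0.272 = 173 planned final deaths.

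**3. Table 15's boundary at 47 deaths.** exp(2 × 0.744/√47) = 1.242. The chances of crossing at HR 0.65, 1, 1.25 and 1.5 are 1.3%, 22.8%, 50.8% and 74.1%, against 1.40%, 22.85%, 52.25% and 74.98% stated. These entries are consistent with 47 deaths and are not in question.

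**4. Expected deaths with N = 448 (224 per arm).** Hazards are λ = ln 2/120 = 0.005776 (control) and 0.65 × 0.005776 = 0.003755 (tafasitamab). The expected proportion dead at calendar month T is 1 − [exp(−λ(T − 21)) − exp(−λT)]/(21λ).
- Month 33.5: control 0.124 × 224 = 27.7; tafasitamab 0.0825 × 224 = 18.5; total 46.2. This reproduces the SAP's 47. With an OS HR of 1 it would be about 55.
- Month 96, followed to end of study: 0.389 × 224 = 87.2 and 0.2745 × 224 = 61.5; total 148.7.
- Month 96, follow-up stopped 72 months after randomization: everyone has reached that limit by month 21 + 72 = 93, so the proportion is 1 − exp(−72λ). This gives 0.340 × 224 = 76.2 and 0.237 × 224 = 53.1; total 129.3.

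**5. Power**, from Φ(|ln 0.65| × √D/2 − 1.96):
- D = 148.7: Φ(2.627 − 1.96) = 74.7%. Allowing for the futility look barely changes it (74.6% at 149 deaths).
- D = 129.3: Φ(2.449 − 1.96) = 68.8%.

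Without the 72-month limit, N = 448 reaches 173 deaths only at about month 114. With it, the count never exceeds 129.

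**6. Other dropout readings** (exponential loss on 528 randomized):

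| Reading | Deaths, month 33.5 | Month 96, no limit (power) | Month 96, 72-month limit (power) |
|---|---|---|---|
| 448 net of dropout | 46.2 | 148.7 (75%) | 129.3 (69%) |
| 528, 15% per 12 months | 46.6 | 107.9 (61%) | 100.1 (58%) |
| 528, 15% over 33 months | 51.4 | 145.1 (74%) | 129.6 (69%) |
| 528, 15% over 96 months | 53.4 | 163.9 (79%) | 144.0 (73%) |
| 528, no dropout | 54.5 | 175.2 (81%) | 152.4 (76%) |

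Only the last row without the limit reaches 80%, and it misses the 47 interim deaths. The two rows that match 47 give 75% and 61% without the limit.

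**7. Effect on the boundary derivation.** The information fraction is 0.27 as used in Table 15, but 47/148.7 = 0.32 or 47/129.3 = 0.36 with N = 448. The same spending function would then give a boundary near HR 1.17 or 1.11, with a 2.3% or 3.4% chance of stopping at true HR 0.65.

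**The case against.** **The 448 reading is not uniquely identified.** SAP 9.2.1 gives no time scale for the 15%, and an annual rate on 528 also matches 47 deaths. With uniform accrual, 448 participants give about 165 PFS events at month 33.5, not 174. Both documents project 338 of 528 FL participants randomized by month 15 (64%, against 71% if accrual were uniform). With accrual slowed to match (a power-curve ramp, which is an assumption), 448 gives 43.4 interim deaths, while 528 with 15% lost over 33 months gives 48.5 deaths and 176 PFS events. This stands as a limit on precision, but it does not bring back 80%. Under that ramp 448 gives 146.6 final deaths (74%), and the better-fitting alternative gives 143.5 (73%).

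**The 15% may not be meant to run to month 96.** The SAP invokes it for the interim count, and survival status can be collected by telephone and from public records. If total loss over 96 months is 15%, power is 79%; with no loss it is 81%. Those readings imply 53 to 55 interim deaths under uniform accrual, so they fit only if the interim and final counts use different loss assumptions, which the SAP does not say.

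**The 80% may be only a design parameter (beta 0.20) of a futility rule, and the trial is not sized on OS.** That is fair as to its role. It is still the only OS power stated, and beta spending is calibrated to it.

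**The 72-month limit is unsettled.** Correct, so the 129-death figure is conditional on which passage governs.

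**Conclusion.** The concern holds. The stated 47 interim deaths, the month-96 final analysis and 80% OS power cannot all come from one dropout assumption. On the reading that fits both 448/528 and the 47 deaths, power is about 75% (149 deaths) with follow-up to end of study, or about 69% (129 deaths) with a limit near 6 years. That is 5 to 11 points below the stated figure. Across all the 15% dropout readings tried, power runs from 58% to 79%, so the exact shortfall depends on a time scale the SAP does not give. A plausible explanation, which cannot be confirmed from the documents, is that dropout was applied to the interim count but not to the final one.

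The figures assume exponential OS and uniform accrual; slower early accrual changes them little. The consequence is limited. Type I error, the sample size and the PFS analysis are untouched, the futility rule is non-binding, and there is no early efficacy look at OS. The power statement and the stated derivation of the boundary are wrong as written.

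**What to change.** 1. Reconcile the survival follow-up passages: Protocol 8.9.3 and 4.2 and SAP 4.1.5 against Protocol 10.4.1.2.3 and 8.9.4 and SAP 7.3.2.3.
2. State one dropout model for OS, with its time scale, and use it for both the interim and the final death counts.
3. Give in Table 15 the deaths expected at the month-96 final analysis and the resulting power: about 69% to 75% on the 448 reading, lower if 15% is meant per year.
4. Then choose one of two routes for the futility rule. Either keep HR 1.24 as a fixed non-binding threshold and stop describing it as the output of an 80%-power beta-spending design, or re-derive the boundary from the corrected information fraction.

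The cost is SAP and Protocol wording plus one rerun of the design software, with no added participants. The stated OS power becomes less favourable. Re-deriving the boundary would raise the chance of a false futility signal at HR 0.65 from 1.4% to about 2.3% or 3.4%; keeping HR 1.24 avoids that.
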